6.3. Handling of Dropouts or Missing Data

Missing data will not be imputed.

In Part B, patients with response that is deemed non-evaluable will be included in the denominator for the purpose of calculating ORR. Non-evaluable patients are patients who do not have a measurable disease at baseline or patients who do not have any post-baseline assessment performed.

6.4. Multicenter Studies

This is a multicenter, non-randomized, open-label study. Enrollment by center and population will be summarized. Because of the limited sample size, endpoint analyses will not be conducted by enrollment center. The investigative center is potentially a prognostic cofactor for efficacy or safety. Therefore, secondary sensitivity analyses using centers or group of centers as a covariate may be performed on selected endpoints to explore whether center have an effect on the efficacy or safety parameters.

6.5. Multiple Comparisons/Multiplicity

No adjustments will be made for multiple comparisons unless otherwise specified.

6.6. Population for Analysis

Safety analyses will be conducted on all patients who have received at least one dose of ramucirumab and/or LY2875358.

Pharmacokinetic analyses will be conducted on patients who have received at least one dose of ramucirumab and/or LY2875358 and have sufficient samples collected to allow the estimation of ramucirumab and/or LY2875358 PK parameters.

Pharmacodynamic analyses will be conducted on patients who have received at least one dose of ramucirumab and/or LY2875358 and have undergone PD assessments.

Efficacy analyses will be conducted on patients who have received at least one dose of ramucirumab and/or LY2875358.

6.7. Patient Disposition

A detailed description of patient disposition will be provided. It will include summaries of the following:

- The number and percentage of patients entered into the study, treated, as well as the number and percentage of patients completing study.
- All patient discontinuations will be documented, and the extent of each patient's participation in the study will be reported. Data on patient discontinuation from study drug and study (overall and by reason for discontinuation) will be listed. If known, a reasons for patients discontinuation will be given.
- All clinically relevant protocol deviations will be listed by pre-determined categories (for example, inclusion/exclusion criteria, non-compliance with protocol procedures, drug dosage/intervention, use of excluded treatments, informed consent/assent process, continuing after meeting withdrawal criteria, or other).

All patients entered into the study will be accounted for in the summary disposition tables. Patients entered into study are patients who signed main informed consent. The number of patients who do not qualify for analysis, who die, or who discontinue before treatment begins will be specified.

Screening failures will be listed and summarized: Information includes number of times of screen failures, subject ID(s) from each screen failure and reason for screen failure. Patients that are deemed eligible that were previously screen failures will also be summarized.

6.8. Patient Characteristics

Patient characteristics for the treated population will include a listing and/or summary of the following:

- Patient demographics, including age, sex, screening height and weight, and screening body mass index, reported using descriptive statistics
- Baseline disease characteristics, including initial diagnosis and ECOG performance status, summarized by presenting frequency counts and percentages
- Prior disease-related therapies if known, including dose, best response, duration of response, date of progression and etc.
- Concomitant medications.

6.9. Treatment Compliance

Ramucirumab and LY2875358 will be administered IV at the investigational site, under the direction of the investigator. As a result, patient's compliance with study drug administration is ensured.

Potential discontinuation of a patient due to study noncompliance (not attending the scheduled visits; see Protocol Attachment 1) will be presented overall as well as for each cycle.

6.10. Concomitant Therapy

Concomitant medications will be summarized for the safety population using the World Health Organization preferred nomenclature. The numbers and percentages of patients reporting concomitant therapies will be provided overall, by type of therapy (surgery, radiotherapy, or systemic therapy), and by drug name.

Prior therapies, including systemic, radiotherapy, and cancer surgeries will be listed and summarized by cohort and overall for all enrolled patients. The Lilly World Health Organization [WHO] Drug Version Dec 2012 B2 or higher will be used to code therapy.

6.11. Safety Analyses

All patients who receive at least 1 dose of ramucirumab and/or LY2875358 will be evaluated for safety and toxicity. Adverse event terms and severity grades will be assigned by the investigator using NCI CTCAE Version 4.03.

Safety analyses will include summaries of the following:

- AEs, including severity and possible relationship to study drugs
- Dose delays and dose adjustments

- Laboratory values
- Vital signs
- DLTs at each dose level
- ECG readings
- Deaths on treatment and within 30 days of treatment discontinuation

Hospitalizations and transfusions during the study treatment period or during the 30-day postdiscontinuation follow-up period will be summarized by study parts.

Dose Limiting Toxicity and Equivalent Toxicity

an AE during Cycle 1 that is possibly, probably, or definitely related to treatment with LY2875358 in combination with a fixed regimen of ramucirumab and fulfills any 1 of the following criterion using the NCI CTCAE Version 4.03:

- \geq Grade 3 non-hematological toxicity. Exceptions will be made for:
 - nausea, vomiting, diarrhea, constipation, or skin rash that persists for ≤ 3 days following appropriate supportive care intervention
 - Grade 3 hypertension in which systolic BP ≥ 160 mmHg and/or diastolic BP ≥ 100 mmHg persist < 7 days after intensified antihypertensive therapy is initiated
- Grade 4 hematological toxicity of ≥ 7 days duration
- \geq Grade 3 thrombocytopenia with \geq Grade 2 bleeding
- Any febrile neutropenia
- Any other significant toxicity deemed by the primary investigator and Lilly clinical research personnel to be dose-limiting (eg, any toxicity that is possibly related to the study medication that requires the withdrawal of the patient from the study during Cycle 1).

Infusion-related reactions (including hypersensitivity reactions and anaphylaxis) should not be considered as DLTs unless the investigator or Lilly medical monitor provides compelling rationale to support their inclusion as a DLT.

Patients in Part A (Cycle 2 or greater) and Part B will be evaluated on an ongoing basis for AEs. In these patients, a DLT-equivalent toxicity will be defined based on trends of any clinical significant toxicity deemed by the study investigators and Lilly clinical research personnel to be dose-limiting and related to study drug(s)s. The investigators and Lilly CRP/CRS will have to agree as to whether such AEs are considered as DLT-equivalent.

Maximum Tolerated Dose

In this study, a 3+3 dose-escalation paradigm will be utilized. If 1 patient, at any dose level,

experiences a DLT during the DLT period (Cycle 1), then up to 3 additional patients will be enrolled at that dose level. If a DLT is observed in ≥ 2 out of 6 patients at any dose level, dose escalation will cease and either the previous dose level will be declared the maximum tolerated dose (MTD) or, following discussions between the investigators and the sponsor, additional patients may be treated at intermediate doses between the previous and the current dose levels.

6.11.1. Extent of Exposure

LY2875358

LY2875358 will be administered after a minimum of a 60-minute observation period (minimum of 30-minute observation period in Cycle 2 and beyond) after the end of the ramucirumab infusion on Days 1 and 15 of a 28-day cycle.

Ramucirumab

Ramucirumab will be dosed prior to the administration of LY2875358 on Days 1 and 15 of a 28-day cycle in Part A and B of this study.

LY2875358 in combination with Ramucirumab

A patient is said to have received a cycle if they received some of the scheduled/planned dose of study treatment in the cycle. A patient is said to have completed a cycle if they received all of study treatment planned for this cycle. The number of patients receiving/completing a given number of cycles will be presented by dose level and overall in a summary table, as well as listed by patient.

The number of dose reductions, dose delays, and number of cycles received will be summarized for all treated patients by parts and by cohorts. The number of patients with any dose reductions and delays will be presented overall as well as for each cycle by parts and cohorts.

6.11.2. Adverse Events

Common Terminology Criteria for Adverse Events (CTCAE) v 4.0 will be used to report AEs. Any minor version of CTCAE Version 4.0 (for example, CTCAE Version 4.03) may be used for this study. Minor updates to the CTCAE Version 4.0 from the NCI will not necessitate a protocol amendment, and the use of an updated CTCAE Version 4.0 will not be considered a protocol violation. For AEs without matching terminology within the NCI-CTCAE v 4.0 criteria, the investigator will be responsible for selecting the appropriate system organ class and assessing severity grade based on the intensity of the event. The verbatim text for these AEs will be coded according to the available version of the Medical Dictionary for Regulatory Activities (MedDRA). For analysis and reporting of AEs, the MedDRA coded terms corresponding to these CTCAE “other-specify” AEs will be used.

A treatment-emergent adverse event (TEAE) is defined as (i) adverse event that occurred after the administration of at least one dose of study therapy, regardless of causality; or (ii) adverse events already present during screening that worsen following exposure to the treatment,

regardless of causality. Event worsen in severity is supported by higher CTCAE grade observed after first dose of study treatment for the corresponding MedDRA lower level term.

The CTCAE term (or MedDRA Lower Level Term (LLT) for cases of CTCAE “other-specify”) will be used in the treatment-emergent determination.

The number of patients who experienced a TEAE, SAE, TEAE related to study drug, died, or discontinued from the study due to an AE will be summarized by treatment. Treatment-emergent adverse events will be summarized by System Organ Class (SOC), by decreasing frequency within SOC, and by maximum CTCAE severity grade, including the total of patients with maximum severity grade ≥ 3 .

Historical illnesses (coded according to the MedDRA dictionary) and pre-existing conditions (using CTCAE terms and severity grades) will be listed by part and by cohort. Historical illnesses are events in the past that ended before the Screening Visit. Pre-existing conditions are events that are present at screening and continue. The pre-existing conditions will be presented by patient and can be combined with the adverse event listing, so that the history of the pre-existing conditions/adverse events can be traced.

6.11.3. Deaths, Other Serious Adverse Events, and Other Notable Adverse Events

Deaths and other serious adverse events will be listed and summarised. Summaries for patients on therapy will include:

- Listing of Patients who Discontinued due to Adverse Events or Death
- Listing of Deaths Reported
- Listing of Serious Adverse Events

Reasons for death will be summarized separately for on-therapy and within 30 days of last dose of study drug/last visit. All SAEs will be summarized by preferred term.

6.11.4. Clinical Laboratory Evaluation

Laboratory data (including chemistry, hematology, coagulation, and urinalysis) will be listed for all patients on therapy. Relevant hematology and chemistry laboratory values will be graded according to CTCAE v4.0. The grades will be included on the listing and summarized by the maximum grade at each cycle over the entire study for all patients on therapy.

Abnormal laboratory results will be listed for all patients on therapy by cycle. To the extent that they can be assessed according to CTCAE v4.0 specific grades, these abnormal lab results will be summarized by cohort and cycle independent of clinical findings determined by the investigator. International System of Units (SI units) will be presented in all outputs.

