#### 10.1.2. Adverse Events

Lilly has standards for reporting AEs that are to be followed regardless of applicable regulatory requirements that may be less stringent. A clinical study AE is any untoward medical occurrence in a patient or clinical investigation subject administered a pharmaceutical product and which does not necessarily have a causal relationship with this treatment. An AE can therefore be any unfavorable and unintended sign (including an abnormal laboratory finding), symptom, or disease temporally associated with the use of medicinal (investigational) product, whether or not related to the medicinal (investigational) product. Any clinically significant findings from labs, vital sign measurements, and so on, that occur should also be reported to Lilly or its designee as

an AE. Lack of drug effect is not an AE in clinical studies because the purpose of the clinical study is to establish drug effect.

The investigator, monitor, and sponsor will review the collected data regularly for evidence of AEs. All patients will be assessed routinely for AEs as outlined in the study schedule. All AEs observed will be graded using NCI-CTCAE Version 4.03.

The NCI-CTCAE Version 4.03 will serve as the reference document for choosing appropriate terminology for, and grading the severity of, all AEs and other symptoms. Any minor version of NCI-CTCAE Version 4.03 (eg, Version 4.0X) may be used for this study. Minor NCI-CTCAE Version 4.03 updates will not necessitate a protocol amendment. For AEs without matching terminology within the NCI-CTCAE Version 4.03 criteria, the investigator will be responsible for selecting the appropriate system organ class and assessing severity grade based on the intensity of the event. Note that both CTCAE term (actual or coded) and severity grade must be selected by study site personnel and collected on the eCRF. This collection is in addition to verbatim text used to describe the AE.

In addition to collecting the AE verbatim, the CTCAE term, and the CTCAE severity grade, AE verbatim text will also be mapped by the sponsor or designee to corresponding terminology within the Medical Dictionary for Regulatory Activities (MedDRA) dictionary.

Cases of pregnancy that occur during maternal or paternal exposures to study drugs should be reported. Data on fetal outcome and breastfeeding should be collected, if feasible, for regulatory reporting and drug safety evaluation.

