Upon documentation of pregnancy, the patient must be removed from the study and treatment with study drug(s) must be stopped immediately.

For all enrolled patients, study site personnel will record the occurrence and nature of each patient's preexisting conditions, including clinically significant signs and symptoms of the disease under treatment in the study. While the patient is on study, site personnel will record any change in these preexisting condition(s) and the occurrence and nature of any AEs. In addition all AEs related to protocol procedures are reported to Lilly or designee.

If a patient's dosage is reduced or treatment is discontinued as a result of an AE, study site personnel must clearly report to Lilly or its designee via eCRF the circumstances and data leading to any such dosage reduction or discontinuation of treatment.

Investigators will be instructed to report to Lilly or its designee their assessment of the potential relatedness of each AE to protocol procedure and/or study drug via eCRF. The investigator decides whether he or she interprets the observed AEs as related to either study disease, study medication, study procedure, or other concomitant treatment or pathologies. To assess the relationship of the AE to the study drug, the following terminologies are defined:

- **Related:** a direct cause and effect relationship between the study treatment and the AE is likely.

- **Possibly related:** a cause and effect relationship between the study treatment and the AE has not been demonstrated at this time and is not probable, but is also not impossible.
- **Unrelated:** without question, the AE is definitely not associated with the study treatment.

As per Lilly's standard operating procedures, all "related" and "possibly related" AEs and SAEs will be defined as related to study drug.

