## Screening/Baseline Assessments

Relative Day Prior to Day 1 of Cycle 1	≤28	≤14	≤7	Comments
Informed Consent	X			Informed consent MUST be signed before performing any protocol procedure
Radiological Tumor Assessment (including head-contrasted CT or brain MRI)	X			These scans can be performed locally and may be from prior to consent if taken within 28 days of Day 1, Cycle 1. PET/CT allowed if CT portion is of diagnostic quality
Chest X-Ray	X			May be omitted in patients having a chest CT for their radiological tumor assessment
Functional Tumor Imaging	X			FDG-PET mandatory in Part B1 (gastric). Further functional tumor imaging (including but not limited to DCE-MRI, FLT-PET) is permitted in all patients if appropriate for the respective tumor type at the discretion of the investigator and considered institutional standard of care or is part of an appropriate imaging study open at the site.
Hepatitis B and C Screening	X			Screening is required (see Attachment 2 ); may be from prior to consent if done within 6 months of Day 1, Cycle 1; Hepatitis B surface antigen and hepatitis C (antibodies or RNA according to local standard)
“Post-Progression Tumor Sample” (baseline)	X			Mandatory (see Section 10.2.1 ); may be from prior to consent if taken within 8 weeks of Day 1, Cycle 1. If this is not available, patient must undergo a tumor biopsy pre-study treatment
Archival Tumor Sample	X			Optional (see Section 10.2.2 )
Medical History		X		Including alcohol/tobacco use/other relevant habits
Physical Examination		X		Including height and body weight
Vital Signs		X		Temperature, blood pressure (seated), heart rate, and respiration rate
Performance Status		X		Per ECOG scale (see Attachment 6 )
CTCAE Version 4.03 Grading (Preexisting Conditions)		X		To be reported only after study eligibility is confirmed. Refer to Section 10.1.2 for reporting expectations.
Concomitant Medications		X		See Section 9.5
Local 12-Lead Electrocardiogram		X		Single ECG
Hematology		X		See Attachment 2
Serum Chemistry including calculated creatinine clearance		X		See Attachment 2
Coagulation		X		See Attachment 2
Urinalysis		X		See Attachment 2
Immunogenicity		X		
Sampling for Exploratory Blood Biomarkers		X		See Section 10.2.2

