	cycle and cycle day -1 is the day before the first dose.
Baseline	For change from baseline analyses, baseline value is defined as the last reported measure on or before the first dose (prior to the dose administration). For change from baseline within a cycle, the measure prior to the first dose of that cycle is baseline. If more than one pre-dose measure is available, they may be averaged if appropriate.
Entered	Patients who sign the informed consent document.
Enrolled	Patients who have been assigned to a treatment (assigned means they received ≥ 1 dose for this study).

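### SAP 6.11.4 tabulates graded laboratory values with no baseline reference, so its tables cannot separate unchanged entry abnormalities from new or worsened ones; a by-cohort shift table would (minor)

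*SAP*

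**What the plan says.** SAP 6.11.4 lists all laboratory data, grades the relevant hematology and chemistry values by CTCAE, and plans two summaries. The first is by maximum grade: "The grades will be included on the listing and summarized by the maximum grade at each cycle over the entire study". The second covers gradeable abnormal results: "these abnormal lab results will be summarized by cohort and cycle independent of clinical findings determined by the investigator". Neither mentions baseline, change or shift. Protocol 12.4 and SAP 6.11 name laboratory values as something to summarize and add nothing further.

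A baseline is available but is not called on here. In Table JTBF.6.1 (SAP 6.1), for change-from-baseline analyses, "baseline value is defined as the last reported measure on or before the first dose". The same entry carries a second rule: "For change from baseline within a cycle, the measure prior to the first dose of that cycle is baseline".

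The protocol foresees abnormal entry values:
- Inclusion criterion [5] allows hemoglobin down to 8 g/dL and platelets down to 75 x 10^9/L in all patients.
- With hepatic metastases or hepatocellular carcinoma, it allows ALT and AST up to 5 times ULN and bilirubin up to 3.0 mg/dL.
- Section 9.2.3.2 gives a rule for patients whose laboratory values at entry are equivalent to Grade 1-2 events.

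**The concern.** A count of graded abnormalities per cycle answers how many patients had an abnormal value. A safety reader wants to know how many became abnormal, or more abnormal, after treatment began. With abnormal values allowed at entry, the two counts differ by an amount that the planned tables do not show.

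This matters more here than in a controlled trial. No cohort has a concurrent comparator against which a constant background rate would cancel, and the Part A dose levels hold 3 to 6 patients each (protocol 8.1.1). Change from entry is then the natural reference. Other parts of the plan use it: SAP 6.11.6 compares ECG values with baseline, the TEAE rule in SAP 6.11.2 requires worsening, and protocol 10.1.4 sets the hepatic monitoring trigger at twice baseline ALT for patients who enter at 3 times ULN or more. The laboratory tables are the exception. At stake is how clearly the tables serve the secondary objective of characterizing safety and toxicity.

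**Working it through.** The plan states no figure for this point, so there is none to reproduce. The check compares texts, sets a bound and gives one illustration.

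**1. What a cell can mean.** For one analyte and one cycle, let g0 be a patient's entry grade and g1 the maximum grade in that cycle. The patient is counted as abnormal if g1 ≥ 1, and is new or worsened only if g1 > g0. If k patients are counted, the number W who are new or worsened satisfies 0 ≤ W ≤ k. For k = 6 in a cohort of 15 (SAP 5.2), W runs from 0/15 = 0% to 6/15 = 40%.

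**2. Where that range applies.** The table is split by grade. If entry grades cannot exceed 2, every patient with g1 of 3 or 4 has worsened, and the count at those grades is unambiguous. The only statement in the documents about entry grade is the Grade 1-2 wording in protocol 9.2.3.2, and criterion [5] caps the main hematologic and hepatic analytes. For those, the ambiguity lies chiefly at Grades 1-2. Other chemistry analytes in Attachment 2, such as sodium, potassium and calcium, have no numeric entry limit. Only the discretionary exclusion [13] restrains them, so the range in step 1 can apply at any grade.

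**3. Illustration under assumption.** Suppose a share b of 15 patients enters with a graded abnormality in one analyte, and a share w of the others develops one. Those who enter abnormal stay unchanged. Shown = 15 x (b + (1 - b) x w); new = 15 x (1 - b) x w.

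| b (assumed) | w = 0: shown / new | w = 10%: shown / new (expected) |
|---|---|---|
| 20% | 3 / 0 | 4.2 / 1.2 |
| 40% | 6 / 0 | 6.9 / 0.9 |
| 60% | 9 / 0 | 9.6 / 0.6 |

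With w fixed at 10%, the number shown rises with b while the number of new cases falls. The w = 0 counts recur in each cycle in which those patients remain on treatment.

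**4. Values drawn before the first dose.** In Attachment 1 the Cycle 1 Day 1 laboratory samples are pre-dose, and footnote c lets local hematology be drawn up to 3 days earlier. Table JTBF.6.1 labels any assessment on the date of first dose as Day 1. A Day 1 pre-dose value can thus be the study baseline and also carry a Cycle 1 day number. SAP 6.11.4 does not say whether it enters the Cycle 1 maximum. Its restriction to patients on therapy describes patients, not values, so it does not settle the matter.

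**5. Other routes to the same information.** Pre-existing conditions are CTCAE-graded at screening (Attachment 1). After that, "site personnel will record any change in these preexisting condition(s) and the occurrence and nature of any AEs". For TEAEs, "Event worsen in severity is supported by higher CTCAE grade observed after first dose of study treatment". Laboratory worsening reported as an adverse event is therefore tabulated against entry. That route runs through the investigator: protocol 10.1.2 asks for clinically significant laboratory findings to be reported, and 9.2.3.2 leaves the clinical significance of asymptomatic Grade 3-4 values to the investigator. The second table in 6.11.4 is meant not to depend on that judgment, and it is a table without a baseline.

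**The case against.** The strongest reply is that nothing in SAP 6.11.4 is wrong. The analyses are descriptive, SAP 6.1 permits further exploratory analyses, and a baseline definition exists if anyone wants to use it. With 3 to 6 patients per dose level and about 15 per expansion cohort, reading the graded listings is practical. Clinically significant worsening should reach the TEAE tables, so what remains uncounted is mostly abnormality judged not clinically significant. Excluding Child-Pugh B and C cirrhosis also narrows entry abnormality in the hepatocellular cohort.

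Much of this stands, and it fixes the weight of the point as minor. It does not remove the gap. A listing gives no count, the adverse event route depends on reporting, and the cirrhosis exclusion leaves the limits in criterion [5] in place.

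Two further objections also stand. The full 0-to-k range should not be claimed for Grade 3-4 counts in analytes with an entry cap, for the reason in step 2 of the working. The fix also means more than a few tables. Attachment 2 lists 10 hematology and 18 chemistry analytes. If 10 to 15 were graded (an assumption), 4 expansion cohorts give 40 to 60 panels, and adding 2 dose levels gives 60 to 90.

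**Conclusion.** The planned laboratory tables cannot separate unchanged entry abnormalities from new or worsened ones. This applies chiefly at low grades for the capped hematologic and hepatic analytes, and at any grade where there is no entry limit. Its actual size is unknown because the documents give no distribution of entry values; the 20%, 40% and 60% shares are assumptions that only illustrate the mechanism.

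A reader might infer more, in two ways that the documents do not support:
- **That a safety signal would be lost or a dose decision distorted.** Escalation rests on DLTs and on review of all safety data (protocol 9.2.2.1 to 9.2.2.3), listings and TEAE tables remain, and the co-primary ORR is untouched.
- **That laboratory worsening is nowhere judged against entry.** The TEAE rule does so for findings reported as adverse events.

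The point is a minor, low-risk improvement to safety reporting.

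**What to change.** Keep both planned tables and add to SAP 6.11.4:

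> For each CTCAE-graded hematology and chemistry analyte, baseline grade versus worst post-baseline grade will be tabulated as a shift table by Part B cohort (Part A by dose level, or by listing only given 3 to 6 patients per level). Baseline is the study baseline in Table JTBF.6.1 (last value on or before first dose, prior to dosing), not the within-cycle baseline. Values drawn before the first dose count as baseline and are excluded from the on-treatment maximum.

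The cost is one standard programmed table per graded analyte and cohort. Using listings alone for Part A keeps the volume down and loses little. Screening and on-study values are already collected, grading is already planned and baseline is already defined, so no new data are needed. Sample size, endpoints and dose rules do not change.
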